---

## **Randomization**

Simple randomization will be centralized and carried out by assigning the 2 treatment options to consecutive computer generated random number obtained through the website  
<http://www.randomizer.at>

The randomization code will be obtained by contacting the number or the [contact] / [name] or by the e-mail address [[contact]](mailto:[contact]) , or [[contact]](mailto:[contact])

Clinical queries during office hours should be directed to one of the clinical coordinators or to an appropriate member of the ReAL trial Management Group

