### **1. Background**

Colorectal cancer (CRC) is the second most common cause of cancer-related death in male and the third in females in Western Countries accounting for more than 500,000 deaths in 2013 worldwide(1).

One of the most worrying postoperative complication in colorectal surgery is the anastomotic leak which can occur in about 10-15% of the cases(2).

This complication severely impact clinical outcomes with increased risk of death or permanent stoma, higher risk of local recurrence) and relevant increase in hospital costs (length of hospital stay, admission to intensive care, re-interventions)(3).

The problem of anastomotic leak is particularly relevant in rectal surgery. The more distal the anastomosis, the higher the likelihood of failure, with resection of a distal rectal cancer having almost a five-fold increased risk of anastomotic leak compared with resection for colon cancer(4).

In fact, anastomotic Leakage (AL) is the most severe complication after Low anterior resection of rectum for cancer, occurring between 3 and 24 % of patients(5).

Many risk factors have been recognized in the onset of this complication(6), including gender (male patient have a higher anastomotic leak rate)(7), malnutrition, obesity an diabet, ASA score, tobacco use, cardiovascular disease, immunosoppression, use of NSAID(8), preoperative pelvis radiation.

Other intraoperative risk factors considered are the splenic flexure mobilization with proximal ligation of the IMA(9), positive intraoperative Air-Leak Test(10) and the perfusion of the anastomosis (11).

Temporary fecal diversion has also been suggested (although a diverting stoma mitigates the clinical consequences of an anastomotic leak but does not prevent it(12).

Other intraoperative technical factors include the use of single or double stapled anastomotic techniques, with or without transanal reinforcing sutures(13).

Therefore, preventing the anastomotic leak can bring benefits to the patient and the health system.

All the risk factors described above rapresent the rationale that justifies the use of intraoperative procedures to prevent the anastomotic leak, such as additional manual stiches to the mechanical suture and / or patches of collagen (proper reinforcement or buttressing) or of sealants.

Several attempts have been proposed to reduce the risk of AL in low rectal cancer surgery including

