### **3.1 General Design**

Prospective, multi-centre, parallel-arm randomized controlled superiority trial. Eligible patients will be randomized to cyanoacrylate reinforcement arm and no reinforcement arm, following rectal anastomosis.

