### 3.2.3 SWOT analysis

STRENGTHS
 
 
- Applicable to anastomosis located over 7 cm from the anal verge
 
- High risk of stoma-related complications
 
- Psychological impact of a stoma
 
- Possibility to improve patient's outcome and reduce hospital costs
 
- Low cost of the new treatment
 
	
WEAKNESS
 
 
- High number of patients to be recruited
 
- Variability of the techniques
 

OPPORTUNITIES
 
 
- Applicable to a relevant proportion of patients affected by Rectal cancer which is one of the most frequent human cancer.
 
- Reduce number of stomas, stoma related complications and new operations for stoma closure
 
- Reduce hospital costs
 
- Improvement of the patients QoL
 
	
THREATS
 
 
- Risk of sepsis for anastomotic leakage (?)
 

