### 3.3 Randomization

Written informed consent will be obtained prior to surgery by the operating surgeon. Computer-generated randomization will be used to create an allocation sequence to assign patients to the different study arms. Randomization will be computer generated and centrally controlled by an operator not involved in the study. Patients will be randomized only after completion of neoadjuvant chemo radiation (when indicated) and before surgery.

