#### **3.5 Participating Institution and Surgeons**

This multicenter trial is opened to the contribution of surgeons across Europe in order to achieve the required number of patient recruitment in the shortest period.

- All surgeons must have prior experience in performing colorectal cancer surgery either in open or laparoscopic route.
- All participating institutions must have IRB (Institutional Review Board)/Ethics Committee approval in order to enroll patients in the trial.
- As part of educational interventions, all participating surgeons will preview a video of the surgical technique of the application of nebulised cyanoacrylate glue.
- Recruitment of Centers will be by direct invitation or spontaneous proposal of Colorectal Units interested in the study.

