## **3.7 ELIGIBILITY CRITERIA**

### **3.7.1 Inclusion Criteria**

- Resectable, histologically proven primary adenocarcinoma of the High-medium rectum without internal and/or external sphincter muscle involvement.
- Distal margin of the tumor at least 8 cm from the anal verge
- Staged as follows prior to neoadjuvant chemoradiation:
  - Stage T2 - T4 at MRI
- Patient classified T3-T4 will undergo neoadjuvant chemoradiation if the cancer is located in the extraperitoneal rectum

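### Allocation is by simple, unstratified randomisation, although centre and chemoradiation status are known at central allocation and could be balanced cheaply

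*Combined protocol and SAP*

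**What the plan says.** The Randomization section specifies the method: "Simple randomization will be centralized and carried out by assigning the 2 treatment options to consecutive computer generated random number". Section 3.3 adds who runs it, "Randomization will be computer generated and centrally controlled by an operator not involved in the study", and when: "Patients will be randomized only after completion of neoadjuvant chemo radiation (when indicated) and before surgery". Neither section, nor any other, mentions blocks, stratification or minimisation.

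The protocol also gives the reasons to balance:

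- Section 1 includes "preoperative pelvis radiation" among the risk factors for leak.
- Section 3.7.1 makes that exposure vary between patients: "Patient classified T3-T4 will undergo neoadjuvant chemoradiation if the cancer is located in the extraperitoneal rectum".
- Section 3.2.3 lists "Variability of the techniques" as a weakness.
- Section 3.5 sets no limit on the mix of centres: "This multicenter trial is opened to the contribution of surgeons across Europe".

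On the analysis side, section 5.2 offers an analysis of covariance to control for important baseline differences, without naming any covariate. It also plans multilevel logistic models for conversion and for complications, without naming centre as a level.

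**The concern.** The trial has two arms, 138 patients and an unstated number of centres. Section 4.2.1 allows more than one anastomotic configuration and leaves bowel preparation to the surgeon. Section 4.3 leaves postoperative care to the surgeon as well. Centre therefore stands for real differences in care, and chemoradiation is a risk factor by the protocol's own account. Simple randomisation leaves the balance of both to chance.

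At the protocol's leak rates the trial expects about 18 leaks. A visible imbalance in radiation or centre would invite doubt about a result resting on so few events. The planned response, adjusting for unnamed baseline differences, leaves room to choose covariates once the imbalances have been seen. Precision and credibility are at stake; validity is not.

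**Working it through.** **Inputs from the documents.** N = 138 (134 + 4), leak rates 16% and 10%, target difference 6 points (section 6.1); simple 1:1 allocation (Randomization section). The plan gives no figure for balance, so there is none to reproduce. N is taken as given; whether it is large enough is a separate question.

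**Assumptions (not in the documents).** Chemoradiation share 20% to 50%; 5, 8 or 10 centres of near-equal size; radiation raises leak risk by 5 to 10 points.

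**1. Expected leaks.** With 69 per arm: 69 × 0.16 + 69 × 0.10 = 17.9.

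**2. Arm totals.** For X ~ Binomial(138, 0.5), the arm-size difference 2X − 138 has SD √138 = 11.7. P(difference ≥ 20) = 10.5%, and the 95% range is 58/80 to 80/58. At 58/80 the variance ratio is (1/58 + 1/80) ÷ (2/69) = 1.026, a 2.6% loss. Averaged over all splits, two-sided power for 16% versus 10% is 17.9%, against 18.0% with equal arms. Arm totals are not the problem.

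**3. Chemoradiation balance.** With share p, the between-arm difference has SD about √(p(1 − p) × 2/69): 6.8 points at p = 0.2 and 8.5 points at p = 0.5. Exact binomial calculation, letting the arm sizes vary:

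| Assumed share | P(differ by ≥ 10 points) | P(differ by ≥ 15 points) |
|---|---|---|
| 20% | 14% | 3.0% |
| 30% | 21% | 5.7% |
| 40% | 24% | 7.3% |
| 50% | 27% | 7.5% |

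**4. Centre balance.** For each centre, take the binomial probability of a 70:30 split or worse, then 1 − ∏(1 − probability):

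- 5 centres (three of 28, two of 27): 1 − (1 − 0.0357)³ × (1 − 0.0522)² = 19.5%.
- 8 centres (two of 18, six of 17): 1 − (1 − 0.0963)² × (1 − 0.1435)⁶ = 68%.
- 10 centres (eight of 14, two of 13): 1 − (1 − 0.1796)⁸ × (1 − 0.0923)² = 83%.

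**5. Effect on the leak difference.** The shift equals the imbalance in the factor times the factor's risk difference. For a 15-point imbalance: 0.15 × 5 = 0.75 points and 0.15 × 10 = 1.5 points, or 12.5% to 25% of the 6-point target. The sampling standard error of the leak difference is √((0.16 × 0.84 + 0.10 × 0.90)/69) = 5.7 points. With a 10-point risk difference and p = 0.5, imbalance contributes an SD of 0.10 × 8.5 = 0.85 points, so (0.85/5.7)² ≈ 2% of the variance.

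**6. After the change.** In simulation, blocks of 4 stratified by chemoradiation kept the arms within 2 patients and the chemoradiation shares within 1.5 points. Blocks of 4 stratified by centre left no centre at 70:30. Stratifying by centre and chemoradiation together gave a 95th percentile of 6 to 8 for the arm-size difference, with a worst case of 8 to 20 for 5 to 14 centres. N stays at 138.

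**The case against.** Simple central randomisation is a defensible choice. It is the least predictable method, and that has value here because the operating surgeon both obtains consent and delivers the treatment. The ordinary test already allows for chance imbalance, the gain in precision is small (step 5), and arm totals hardly matter (step 2). All of that stands, and it is why this is only an improvement to the design.

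A reader might infer that a 10-point imbalance in a risk factor rivals the 6-point target. It does not: one is a difference in factor prevalence, the other a difference in leak rate. With a 10-point risk difference, a 6-point shift would need an imbalance of 6/0.10 = 60 points, about seven SDs at p = 0.5. Even if every leak fell in the exposed half (26% against 0%, at a mean rate of 13%), it would need 6/0.26 = 23 points, with a probability of about 0.7%.

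It may also be said that section 5.2 already handles the matter by adjustment. It does so only in part. No covariate is named, and centre does not appear. When covariates would be chosen is not stated, so choice after seeing the data is possible but not established.

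Finally, with about 18 leaks, a separate fixed term for each of many centres would be unstable. That objection is sound and shapes the fix.

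**Conclusion.** The point holds as a cheap improvement. The plan leaves to chance two factors whose importance the protocol itself signals and which are known at allocation. Moderate imbalance is fairly likely: 14% to 27% for a chemoradiation gap of 10 points or more, and about 20% to 83% for at least one centre at 70:30 or worse. The consequence for the leak estimate is modest: 0.75 to 1.5 points for a 15-point gap, which itself has a 3% to 7.5% chance.

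These figures rest on the assumed chemoradiation share, centre number and size, and radiation effect. The documents give none of these, and they do not quantify the effect of centre on leaks at all. They do not support a reading that the randomisation is biased or invalid, or that unequal arms would materially weaken the trial.

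**What to change.** In the Randomization section, keep central computer-generated allocation but stratify by centre and neoadjuvant chemoradiation (yes/no), using permuted blocks of randomly varying, undisclosed size. If many small centres are expected, use minimisation with a random element, because centre-by-chemoradiation strata would become thin.

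In section 5.2, prespecify the same factors in the primary leak analysis: chemoradiation as a fixed term, and centre as a random effect or through a stratified test. This replaces adjustment for unnamed baseline differences.

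The cost is a setting in the randomisation system and a sentence in each section, with no change to N. The documents do not describe what the randomisation service can do, so its capability must be confirmed. The downside is slightly more predictable allocation within a centre, limited by varying block sizes or the random element and by central release. The full benefit requires the change before enrolment starts.

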### **1. Background**

Colorectal cancer (CRC) is the second most common cause of cancer-related death in male and the third in females in Western Countries accounting for more than 500,000 deaths in 2013 worldwide(1).

One of the most worrying postoperative complication in colorectal surgery is the anastomotic leak which can occur in about 10-15% of the cases(2).

This complication severely impact clinical outcomes with increased risk of death or permanent stoma, higher risk of local recurrence) and relevant increase in hospital costs (length of hospital stay, admission to intensive care, re-interventions)(3).

The problem of anastomotic leak is particularly relevant in rectal surgery. The more distal the anastomosis, the higher the likelihood of failure, with resection of a distal rectal cancer having almost a five-fold increased risk of anastomotic leak compared with resection for colon cancer(4).

In fact, anastomotic Leakage (AL) is the most severe complication after Low anterior resection of rectum for cancer, occurring between 3 and 24 % of patients(5).

Many risk factors have been recognized in the onset of this complication(6), including gender (male patient have a higher anastomotic leak rate)(7), malnutrition, obesity an diabet, ASA score, tobacco use, cardiovascular disease, immunosoppression, use of NSAID(8), preoperative pelvis radiation.

Other intraoperative risk factors considered are the splenic flexure mobilization with proximal ligation of the IMA(9), positive intraoperative Air-Leak Test(10) and the perfusion of the anastomosis (11).

Temporary fecal diversion has also been suggested (although a diverting stoma mitigates the clinical consequences of an anastomotic leak but does not prevent it(12).

Other intraoperative technical factors include the use of single or double stapled anastomotic techniques, with or without transanal reinforcing sutures(13).

Therefore, preventing the anastomotic leak can bring benefits to the patient and the health system.

All the risk factors described above rapresent the rationale that justifies the use of intraoperative procedures to prevent the anastomotic leak, such as additional manual stiches to the mechanical suture and / or patches of collagen (proper reinforcement or buttressing) or of sealants.

Several attempts have been proposed to reduce the risk of AL in low rectal cancer surgery including

suture protection with omental flap and external suture reinforcement by biological glue or mesh (14-16).

Some Authors have reported good results of reinforcement of the colon anastomosis with cyanoacrylate glue. in a porcine model(17, 18).

Cyanoacrilate is a synthetic glue with sealing, adhesive and hemostatic properties widely used in surgery. Furthermore the sealing effect creates an antiseptic barrier against bacteria (19).

Several clinical studies have described the utility of cyanoacrylate glue mainly in vascular surgery, urology(20, 21) and bariatric surgery (22).

Considering its mechanical, physical, biological properties and its safety, cyanoacrylate glue could facilitate the healing of the colorectal anastomosis reducing leak rate, without negative effects on perfusion(23).

## **2. Study hypothesis**

The hypothesis is that the application of nebulized cyanoacrylate to the colo-rectal anastomosis in open or laparoscopic/robotic rectal surgery can prevent the leakage

### **3.1 General Design**

Prospective, multi-centre, parallel-arm randomized controlled superiority trial. Eligible patients will be randomized to cyanoacrylate reinforcement arm and no reinforcement arm, following rectal anastomosis.

### **3.2 Endpoints**

#### **3.2.1 Primary**

The aim of the trial is to observe a significantly lower number of anastomotic leak of a colorectal anastomosis in the group of patients treated with cyanoacrylate glue

### 3.2.2 Secondary

**SAFETY:** Demonstration that the new treatment will not add related morbidity

**EFFICACY:** Demonstrate that anastomotic reinforcement with cyanoacrylate decrease the rate of anastomotic leakage

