### **3.6.2 Classification of the postoperative complications**

- The Clavien Dindo Classification for postoperative complications will be adopted (see attached form 9.2)
- The Comprehensive Complication Index

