#### **4.2.1.1 NO CYANOACRYLATE GROUP**

Patients selected in the no cyanoacrylate glue arm will not have anastomotic reinforcements

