## **6 STATISTICAL ANALYSIS**

### **6.1 Sample Size Determination:**

The mean percentage of anastomotic leak after rectal cancer is 16% and its reduction to 10% is considered to be clinically significant. Therefore, the interval of confidence calculated is 12. A sample size calculation shows that 67 subjects per arm will suffice for accepting of the hypothesis with a power of 0.8 and a type I error probability of 0.05, with a Confidence level of 95% (sample size calculated by R Studio Version 1.1.419 – © 2009-2018 RStudio, Inc.). Accounting for a predicted 5% estimated loss to follow-up, a total of 138 (134+4) patients will be included in the study.

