### **5.2 Statistical Methods:**

All statistical analysis will be done in an intention-to-treat fashion. No interim analyses are planned. For all statistical tests, a P value of .05 will be considered significant. A Student t-test will provide an unadjusted estimate of the difference between treatment arms. Analysis of covariance, a more robust method that allows control for key differences in baseline characteristics, will be used to provide adjusted comparisons.

Like the primary outcome, continuous secondary outcomes (such as safety and efficacy) will be modeled by t-tests and analysis of co-variance.

Any relationship of the anastomotic leakage with other possible adverse factors will be evaluated by univariate and multivariate regression analysis

When the complete case analysis will exclude more than 5% of patients due to missing data, exploratory analyses to investigate the effect of missing data will be performed. In order to explore the mechanism of the missing data and the validity of a complete case analysis for each end point, patient characteristics will be compared between those with and without missing data and multilevel logistic regression models will be used to identify any associations between prognostic variables and to inform if data are missing at random.

Multilevel logistic regression will be used to estimate the odds ratios (ORs) for conversion to laparotomy, intraoperative complications, and postoperative complications between treatment groups.

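### The secondary safety aim is to demonstrate no added morbidity, but the plan has only difference tests and odds ratios, with no margin or confidence-bound rule that could support that conclusion

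*Combined protocol and SAP*

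**What the plan says.** Section 3.2.2 (Secondary) gives the safety aim in one line: "Demonstration that the new treatment will not add related morbidity". Section 3.1 describes a "parallel-arm randomized controlled superiority trial" and names no non-inferiority component.

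The analysis is in section 5.2 (Statistical Methods):

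- On secondary outcomes: "continuous secondary outcomes (such as safety and efficacy) will be modeled by t-tests and analysis of co-variance".
- On complications, multilevel logistic regression "will be used to estimate the odds ratios (ORs) for conversion to laparotomy, intraoperative complications, and postoperative complications between treatment groups".
- On decisions: "For all statistical tests, a P value of .05 will be considered significant".

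Section 3.6.1 defines adverse events. Section 3.6.2 adopts the Clavien-Dindo grading and "The Comprehensive Complication Index". Section 6.1 (Sample Size Determination) sizes the trial on anastomotic leak and says that "67 subjects per arm will suffice for accepting of the hypothesis". Section 6.3 (Data Safety Monitoring Committee) allows the board's chair to suggest termination if complication rates are unacceptable, without a number.

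**The concern.** Demonstrating that a treatment adds no morbidity is a no-harm conclusion. It needs a statement of how large an increase must be ruled out, or at least a rule for reading the upper confidence limit. A test of difference can show that morbidity was added. When it fails to reject, it shows only that the data did not establish an increase.

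The final report will have to answer the aim in section 3.2.2, and the plan names no result that would do so. The only criterion available is P = .05, so a non-significant comparison could easily be written up as the promised demonstration. For a product applied to the anastomosis, that could mislead readers about safety, particularly with few patients per arm.

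**Working it through.** **1. Search for a rule.** Each place where a margin or bound might stand was checked.

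- Section 3.2.2: states the aim, with no limit.
- Section 3.1: superiority only.
- Sections 3.6.1 and 3.6.2: define and grade events, with no between-arm threshold.
- Section 5.2: difference tests and odds ratios. No confidence intervals are mentioned for them.
- Section 6.1: the 95% level and the interval of 12 belong to the leak sample size, not to morbidity.
- Section 6.3: a monitoring provision without a numerical limit. It does not govern the final conclusion.

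None supplies the rule.

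**2. The plan's own size.** The only size stated is 67 per arm, for leak. With section 6.1's inputs (16% v 10%, power 0.8, alpha .05 taken as two-sided), the pooled two-proportion formula gives

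n = [1.96·√(2·0.13·0.87) + 0.8416·√(0.16·0.84 + 0.10·0.90)]² / 0.06² = (0.932 + 0.399)² / 0.0036 ≈ 492 per arm.

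So 67 is not reproduced. That is a separate problem. The precision of the safety comparison is therefore shown at both sizes.

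**3. Precision at 67 per arm.** Control morbidity p is assumed to be 10% to 40%, because the documents give no rate.

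- Half-width of the 95% CI for the risk difference, equal rates: 1.96·√(2p(1−p)/n). At p = 0.10: 1.96·√(0.18/67) = 0.102. At p = 0.40: 1.96·√(0.48/67) = 0.166.
- Chance that a true increase d is non-significant, with q = p + d and m = (p + q)/2: Φ{[1.96·√(2m(1−m)/n) − d] / √([p(1−p) + q(1−q)]/n)}. At p = 0.10, d = 0.10: Φ[(0.1209 − 0.10)/0.0611] = Φ(0.342) = 0.634. At p = 0.40, d = 0.10: Φ[(0.1685 − 0.10)/0.0855] = Φ(0.801) = 0.788.
- Upper 95% limit of the odds ratio when observed rates are equal: exp{1.96·√(2/[np(1−p)])}. At p = 0.10: exp(1.129) = 3.09. At p = 0.40: exp(0.691) = 2.00.

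| Assumed control morbidity | CI half-width (points) | True +10 points non-significant | True +5 points non-significant | OR upper limit, equal observed rates |
|---|---|---|---|---|
| 10% | 10.2 | 63.4% | 86.2% | 3.09 |
| 20% | 13.5 | 73.5% | 89.8% | 2.33 |
| 30% | 15.5 | 77.4% | 91.1% | 2.09 |
| 40% | 16.6 | 78.8% | 91.6% | 2.00 |

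**4. The same formulas at 492 per arm.** The half-width falls to 3.7 to 6.1 points. A true 10-point increase is missed 0.7% to 11.5% of the time, and a true 5-point increase 34.0% to 64.6% of the time. A larger trial narrows what a null result leaves open. It still does not say which increase has to be excluded.

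**The case against.** The strongest reply is that this is one line under a secondary heading, and that its verb is loose phrasing for assessing safety. The efficacy line beside it uses the same verb for an aim that repeats the primary. The plan also does much of what a surgical trial usually does on safety: it defines events, grades severity, estimates complication odds ratios and sets up a monitoring board. A fitted logistic model yields standard errors, so intervals are within easy reach. All of this stands. It limits the point to the wording and reporting of the aim, but does not supply the missing basis for a demonstration.

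It is also fair to say that the large percentages owe much to 67 per arm and to an assumed morbidity range, and that the formulas are normal approximations, not the planned multilevel or covariance models. The figures are therefore approximate. The logical gap does not depend on them.

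A reader might infer three stronger things that the documents do not support:

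- **That the sponsor intends to treat P > .05 as proof of safety.** No section says so.
- **That the undefined word 'related' makes the aim unanswerable**, because glue-related events should not arise where "Patients selected in the no cyanoacrylate glue arm will not have anastomotic reinforcements". In a randomised comparison, the between-arm difference in all-cause morbidity is itself the estimate of what the glue adds. Case-by-case attribution is not needed.
- **That safety is left unexamined.** Sections 3.6.1, 3.6.2, 5.2 and 6.3 show otherwise.

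**Conclusion.** The point holds as a mismatch between a stated conclusion and the methods given to reach it. As written, the plan can detect or estimate added morbidity but has no rule by which it could demonstrate that none was added. This is true at any sample size.

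At the stated 67 per arm, a null comparison would say little: the half-width is about 10 to 17 points, and a true 10-point increase is non-significant about 63% to 79% of the time. These sizes rest on an assumed control morbidity of 10% to 40%, a binary outcome, two-sided testing at .05 (the plan does not state sidedness), a normal approximation and no allowance for centre effects. They do not describe the continuous complication index.

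The aim is secondary and the primary analysis is untouched. The correction is still worth making, because it changes what the trial may claim about safety.

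**What to change.** - **Section 3.2.2:** replace the safety aim with one of estimation, for example: *to estimate the between-arm difference in postoperative morbidity, graded as in section 3.6.2 and including the Comprehensive Complication Index, with 95% confidence intervals*.
- **Section 5.2:** state that the odds ratios and differences for safety outcomes are reported with 95% confidence intervals, and that P > .05 will not be taken as showing no added morbidity.

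The cost is a few lines of text, with no added patients, visits or data. The price is a more modest safety conclusion: the report can say how large an increase the data leave open, but not that there is none. If the sponsor wishes to keep the word demonstration, it would have to prespecify and justify a morbidity endpoint, a margin and a confidence-bound rule, and check the sample size against them.
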